2. LIST OF ABBREVIATIONS

ACE	angiotensin-converting-enzyme inhibitor
AE	Adverse Event
AF	Atrial Fibrillation
ARB	Angiotensin receptor blockers
BIPi	Boehringer Ingelheim Pharmaceuticals Inc
CDR	Clinical data repository
CHA ₂ DS ₂ -VASc	Congestive heart failure, Hypertension, Age \geq 75 years (doubled), Diabetes mellitus, Stroke (doubled), Vascular disease, Age 65–74 years, Sex category
CHADS ₂	Congestive heart failure, Hypertension, Age \geq 75 years, Diabetes mellitus, Prior Stroke or TIA or Thromboembolism
CCI	Charlson comorbidity index
CI	Confidence Interval
COPD	Chronic objective pulmonary disease
DEERS	Defense eligibility enrollment reporting system
DoD	Department of Defense
DRG	Diagnosis-related group
EMR	electronic medical record
ER	emergency room
FDA	Federal drug administration
FFS	fee-for-service
GERD	Gastroesophageal reflux disease
GI	Gastrointestinal
GIH	gastrointestinal hemorrhage
HASBLED	Hypertension, Abnormal renal/liver function, Stroke, Bleeding history or predisposition, Labile International Normalized Ratio, Elderly, Drugs/alcohol concomitantly
HIPAA	health insurance portability and accountability act
HIV	Human immunodeficiency virus

Proprietary confidential information © 2016 Boehringer Ingelheim International GmbH or one or more of its affiliated companies

HMO	health maintenance organization
████████	
ICD	International classification of diseases
ICH	intracerebral hemorrhage
IPTW	Inverse probability to weighting
IR	Incidence Rate
IRB	Institutional Review Board
████████	
KM	Kaplan-Meier
MB	Major bleed
MDR	Military health system data repository
MHS	Military health system
████████	
MTF	military treatment facilities
N	Number
NDC	National drug code
NVAF	Non-valvular Atrial Fibrillation
NOAC	Non-Vitamin K antagonist oral anticoagulant
NSAID	Non-steroidal anti-inflammatory drug
OV	office visit
PDTS	Pharmacy data transaction system
████████	
PPI	Proton pump inhibitor
PPO	preferred provider organization
PSM	Propensity score matching
PS	Propensity Score
PSTAT	Project Statistician
PY	Person-years at risk

RCT Randomized controlled trial

RR Rate Ratio

SD Standard deviation

SAS Statistical analysis software

TIA transient ischemic attack

Tx Treatment

VPN Virtual private network

[REDACTED]

[REDACTED]

4. ABSTRACT

Name of company: Boehringer Ingelheim			
Name of finished medicinal product: Pradaxa			
Name of active ingredient: dabigatran etexilate			
Protocol date: 15Dec2016	Study number: 1160.274	Version/Revision: 1.0	Version/Revision date: N/A
Title of study:	The Comparative Safety and Effectiveness of dabigatran, versus rivaroxaban, and apixaban Utilized in the Department of Defense (DoD) Non-Valvular Atrial Fibrillation Patient Population-A Retrospective Database Analysis		
Rationale and background:	
Due to the emergence of multiple pharmaceutical alternatives to warfarin, physicians in the US are faced with many anticoagulation options. To help inform their decisions physicians want to know the comparative safety and efficacy profiles of these new agents.
 
Now that real world experience with dabigatran for NVAF patients has accrued, the safety and effectiveness for dabigatran, rivaroxaban, and apixaban may also be assessed and compared in this setting.
 
Boehringer Ingelheim Pharmaceuticals Inc. (BIPI) has an opportunity to collaborate with DoD to conduct comparative safety and effectiveness studies of dabigatran, rivaroxaban, and apixaban using already existing real world data from DoD's claims and EMR data.
		
Research question and objectives:	
To assess the safety and effectiveness of newly initiated dabigatran among patients diagnosed with NVAF in comparison to newly initiated rivaroxaban users and newly initiated apixaban users in two (2) separate study cohorts:
 
 • dabigatran vs. rivaroxaban • dabigatran vs. apixaban 		
Study design:	Non-interventional study based on existing data with propensity score matching (PSM)		
Population:	NVAF patients, \geq 18 years of age, enrolled within the DoD Military Health System (MHS) who have newly initiated dabigatran, rivaroxaban or apixaban. Patients must be treatment naïve from OAC use prior to first (index) NOAC.		

Variables:	
Covariates
 
 • Gender • Age • Geographic location • Health plan type • Baseline comorbid conditions • Pre-index medication use • NOAC prescribing provider type • Baseline Charlson comorbidity index • Baseline stroke risk (CHADS₂ and CHA₂DS₂-VASC) • Baseline bleeding risk (modified HAS-BLED) • Index exposure • Time to index exposure • Duration of follow-up 
Primary outcomes
 
 • Stroke overall (hemorrhagic, ischemic, uncertain) • Major bleeding, overall 
Secondary outcomes
 
 • Ischemic stroke • Hemorrhagic stroke • Major intracranial bleeding • Major extracranial bleeding 
 ◦ Major GI bleeding ◦ Major other bleeding • TIA • All-cause mortality 
Data sources:	Military Health System Data Repository (MDR)
Study size:	
Initial study feasibility counts show newly initiated dabigatran among patients diagnosed with NVAF in comparison to newly initiated rivaroxaban users and newly initiated apixaban users in two (2) separate study cohorts:
 
 • dabigatran (n= 16,604) vs. rivaroxaban (n=25,215); July 1, 2011 to June 30, 2016 • dabigatran (n=6,050) vs. apixaban (n=20,930); December 28, 2012 to June 30, 2016 
These numbers are based on initial inclusion/exclusion criteria as

	
specified above. Additional inclusion/exclusion criteria will reduce population sizes further but feasibility estimates provide strong support for necessary sample size.

Data analysis:	
The target population will include OAC treatment naïve NVAF patients with at least one prescription claim for dabigatran, rivaroxaban or apixaban. For each patient treated with a NOAC, the date of the first NOAC prescription (index exposure) will serve as the index date. Only those patients whose index date occurs between the respective study periods will be included. The 12-month period prior to the index date will be defined as the pre-index period. The patients will be required to have a NVAF diagnosis in the pre-index period (including index date).
 
Study period NOT including pre-index period:
 
 • Dabigatran vs. Rivaroxaban: July 1, 2011 to June 30, 2016 • Dabigatran vs. Apixaban: December 28, 2012 to June 30, 2016 
Study period including pre-index period:
 
 • Dabigatran vs. Rivaroxaban: July 1, 2010 to June 30, 2016 • Dabigatran vs. Apixaban: December 28, 2011 to June 30, 2016 
Standard dosing for each NOAC will be used for main analyses. All doses for each NOAC will be combined for a sensitivity analysis. Standard dose for NOAC's:
 
 • Dabigatran 150 mg, twice daily, total daily dose of 300 mg • Rivaroxaban 20 mg, once daily, total daily dose of 20 mg • Apixaban 5 mg, twice daily, total daily dose of 10 mg 
Length of Follow-up:
 
The post-index follow-up period will begin the day following the NOAC index date and end on whichever of the following occurs earliest:
 
 • The day of discontinuation of the index NOAC exposure; • The day before a switch to an anticoagulant different from the index exposure; • The day before a change in dose for the index NOAC; • The end of continuous eligibility of a patient in the health plan (disenrollment); • The end of the study observation period; or • The date of death of the patient. • The last date of calculated days supplied if treatment gap


>30 days
 
Patients need at least two days of exposure to the index NOAC to ensure they had at least one day of index NOAC exposure in the post-index follow-up period. A sensitivity analysis will also be performed using a 14 day treatment gap.
 
Both claims-level data, including diagnosis codes, procedure codes, pharmacy dispensed drugs, cost information, and enrolment data, as well as EHR-level data, including relevant lab tests and results, will be extracted for all applicable patients. Patient demographics, treatment history, and comorbidities, will be derived from the electronic database. Start and stop dates of each course of treatment will be coded from the pharmacy and medical claims data using rules to be developed in the study protocol. Comorbidities of interest will be ascertained through ICD-9 and ICD-10 diagnosis codes, in combination with procedures and medications, as appropriate to the study protocol definitions.
 
To account for potential selection bias, the study cohorts (dabigatran/rivaroxaban and dabigatran/apixaban) will be matched on their baseline characteristics using the propensity score matching (PSM) method. The PSM aims to balance the two treatment groups on baseline demographics, health plan type and clinical characteristics. The feasibility of PSM will be evaluated based on available sample size and descriptive results. If patient characteristics between dabigatran/rivaroxaban and dabigatran/apixaban cohorts are significantly different, i.e., less than 50% of patients in the dabigatran group can be matched to the rivaroxaban or apixaban group based on PSM, then the study design will be re-evaluated before proceeding to analysis. The Nearest Neighbor method of propensity score matching within a caliper of 0.10-0.20 (depending on resulting sample sizes) of the standard deviation of the estimated logit will be used to select the matched samples.
 
The propensity score models will include baseline variables known to be confounders or factors related to the outcome only, including age, gender, health plan type, geographic region, month and year of index date, Charlson comorbidity index (CCI), stroke risk scores (i.e. CHADS₂ or CHA₂DS₂-VASc), bleeding risk scores (i.e., modified HAS-BLED), specified comorbid conditions and medication use, based on literature and clinical relevance, as well as empirical data (top diagnoses, procedures, etc.) that may account for possible unforeseen confounding.

--

Descriptive Statistics

Patient characteristics, including demographics, will be reported for NVAF patients treated with dabigatran, rivaroxaban, or apixaban. Stroke risk will be quantified using the CHADS₂, CHA₂DS₂-VASc score and bleeding risk through the HAS-BLED score. Other descriptive variables may include the following:

Comorbid conditions at baseline:

- Cancer
- Rheumatoid arthritis
- Coronary artery disease
- Acute myocardial infarction
- Cardiomyopathy
- Ischemic stroke
- Stroke (all types)
- TIA
- Congestive heart failure
- Left ventricular heart failure
- Hypertension
- Peripheral artery disease
- Liver disease
- Renal disease
- COPD/emphysema
- Diabetes
- Peptic ulcer (bleeding or non-bleeding)
- GERD
- Venous thromboembolism
- Hyperlipidemia
- HIV infection
- Bone marrow disease (thrombocytopenia, chronic anemia, myelofibrosis)
- Coagulopathy (hemophilia, Von Willebrand disease)
- Chronic kidney disease

Medication History and Concomitant Use:

- **Non-Oral Anticoagulants:** Number of prescription fills (normalized to a 30-day supply) will be captured during the pre-index period (See [Appendix A, Table 8](#))
 - Argatroban (can be used in procedures in lieu of heparin)
 - Unfractionated Heparin (Heparin)
 - Low Molecular Weight Heparins:
 - Enoxaparin
 - Tinzaparin

	
▪ Dalteparin▪ Fondaparinux• Other medication use: Use of other medications will be determined if patients had ever filled a medication in the following drug classes during the pre-index period (See Appendix A, Table 3, Table 8).
○ Beta blockers○ Calcium channel blockers○ Diuretics○ Other antihypertensives (i.e., angiotensin-converting-enzyme (ACE) inhibitors, combinations)○ Antihyperlipidemics○ Corticosteroids○ Antidiabetics○ Antiarrhythmics (Amiodarone HCl, Propafenone and Flecainide, Dronedarone, Betapace (Sotalol), Tikosyn, Disopyramide (Norpace), Quinidine)○ Ketoconazole○ Antiplatelets (e.g., dypiridamole, aspirin, etc.)○ NSAIDs
--	--

Outcome Analysis

The follow-up period, which comprises the patient-time denominator, will start at index and will be censored at the first occurrence of either of the following:

- outcome event
- switch to another anticoagulant
- change in dose of index NOAC
- discontinuation of therapy, as defined as a gap in therapy exceeding 30 days (a 14 day gap sensitivity analysis will also be performed)
- end of DoD eligibility
- end of study period

Primary outcomes

- Stroke overall (hemorrhagic, ischemic, uncertain)
- Major bleeding, overall

Secondary outcomes

[figure not shown]
- Ischemic stroke
- Hemorrhagic stroke
- Major intracranial bleeding
- Major extracranial bleeding
 - Major GI bleeding
 - Major other bleeding

- TIA
- All-cause mortality

The first occurrence of each outcome will be identified, separately. For each outcome, event rates and 95% confidence intervals (CI) will be calculated using a person-time approach for each treatment and further stratified by age and gender. Time-to-event analyses (i.e. Kaplan-Meier analysis and Cox proportional hazards model analysis) will be performed for each treatment comparison. Details will be laid out in the protocol and approved by the [REDACTED]-DoD-BIPI study teams.

Sensitivity, subgroup and/or exploratory analyses will be performed and may impact changes to the definitions to the assigned cohort, covariates, or outcome. Potential sensitivity/subgroup/exploratory analyses are below:

Milestones:	Protocol Completion Data Extraction, Preparation, and QA Data Analysis Develop Final Report
--------------------	--

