- Valvuloplasty, tricuspid valve; with ring insertion
- Replacement, tricuspid valve, with cardiopulmonary bypass

Standard dosing for each NOAC will be used for main analyses. All doses for each NOAC will be combined for a sensitivity analysis. Standard dose for NOAC's include:

- Dabigatran 150 mg, twice daily for total daily dose of 300 mg
- Rivaroxaban 20 mg, once daily for total daily dose of 20 mg
- Apixaban 5 mg, twice daily for total daily dose of 10 mg

Length of Baseline

The 12-month period prior to and including the NOAC index date will be defined as the baseline period. Patients will be required to have an NVAF diagnosis during this baseline period.

The pre-index period will serve as a look-back period to measure baseline covariate data and apply other inclusion and exclusion criteria.

Length of Follow-up:

The post-index follow-up period will begin the day following the NOAC index date and end on whichever of the following occurs earliest:

- The day of discontinuation of the index NOAC exposure;
- The day before a switch to an anticoagulant different from the index exposure;
- The day before a change in dose for the index NOAC;
- The end of continuous eligibility of a patient in the health plan (disenrollment);
- The end of the study observation period; or
- The date of death of the patient.

Patients need at least two days of exposure to the index NOAC to ensure they had at least one day of index NOAC exposure in the post-index follow-up period.

For patients, index exposure will be considered discontinued if there is a treatment gap longer than the 30 day allowable gap specified from the end of the calculated days supplied.

Patients that have treatment gap longer than the specified allowable gap will be censored at that point and follow-up will be discontinued. A sensitivity analysis will also be performed using a 14 day treatment gap.

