9.3.2 Outcomes

The outcomes will be assessed during the post-index period for the two cohorts. If a patient discontinued the index NOAC or switched to a different NOAC, the outcomes assessment would not continue beyond the date of discontinuation or the switch. The primary and secondary outcomes assessed will be safety and effectiveness measures as described below in the [Outcomes of Interest table](#).

The safety and effectiveness analysis will be conducted for the following cohorts:

- Oral Anticoagulant treatment naive patients: Dabigatran vs. Rivaroxaban
- Oral Anticoagulant treatment naive patients: Dabigatran vs. Apixaban

Outcomes of Interest	
Primary	Stroke (hemorrhagic, ischemic, uncertain classification) Major bleeding
Secondary	Major bleeding, by the following sites 
 • Major intracranial • Major extracranial 
 ◦ Major gastrointestinal ◦ Other Stroke by type 
 • Ischemic stroke • Hemorrhagic stroke Transient ischemic attack (TIA) All-cause mortality
Further	[REDACTED]

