- discontinuation of therapy, as defined as a gap in therapy exceeding 30 days
- end of DOD eligibility
- end of study period

[figure not shown]
Patients need at least two days of exposure to the index NOAC to ensure they had at least one day of index NOAC exposure in the post-index follow-up period.

For patients, index exposure will be considered discontinued if there is a treatment gap longer than the 30 day allowable gap specified from the end of the calculated days supplied.

Patients that have treatment gap longer than the specified allowable gap will be censored at that point and follow-up will be discontinued. A sensitivity analysis will be performed on patients that have treatment gaps longer than 14 days to determine if an adjustment to the gap days is necessary.

The first occurrence of each outcome will be identified, separately. For each outcome, event rates and 95% confidence intervals (CI) will be calculated using a person-time approach for each treatment and further stratified by age and gender. To compare the occurrence of each outcome between treatments, Kaplan-Meier analysis and Cox proportional hazards model analysis will be performed. Additional adjustments will be made for baseline variables that are not sufficiently balanced after PSM.

Standard dosing for each NOAC will be used for main analyses. All doses for each NOAC will be combined for a sensitivity analysis as defined below.

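### The abstract's supply-end censoring date drops events in an unbridged refill gap but keeps bridged gap time, which lowers event rates; sections 9.2 and 9.7.1 leave the date open

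*Combined protocol and SAP*

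**What the plan says.** Four places bear on when follow-up ends for a patient who stops refilling.

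- **Section 4, Length of Follow-up**, gives the window: "The post-index follow-up period will begin the day following the NOAC index date and end on whichever of the following occurs earliest". Its list contains the day of discontinuation and, as a separate item, "The last date of calculated days supplied if treatment gap", which the text completes as more than 30 days. This is the only item anywhere that attaches an explicit date to a long gap.
- **Section 9.2, Length of Follow-up:** the same list without the supply-end item. Discontinuation is a "treatment gap longer than the 30 day allowable gap specified from the end of the calculated days supplied", and then: "Patients that have treatment gap longer than the specified allowable gap will be censored at that point and follow-up will be discontinued". No date is given. Section 9.7.1 repeats this.
- **Person-time, in section 4 (Outcome Analysis) and section 9.7.1:** "The follow-up period, which comprises the patient-time denominator, will start at index and will be censored at the first occurrence" of several events. These include the outcome itself and "discontinuation of therapy, as defined as a gap in therapy exceeding 30 days". A shorter gap is not on the list, so its days stay in the denominator.
- **Section 9.3.2:** after stopping or switching, "the outcomes assessment would not continue beyond the date of discontinuation or the switch".

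A sensitivity analysis shortens the permitted gap to 14 days.

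**The concern.** Under the abstract's date, whether a gap day is at risk is settled by what happens afterwards. If the gap is bridged by a refill, its days count. If it runs past 30 days, follow-up is moved back to the day supply ended, and anything that happened in the gap falls outside it. A major bleed or stroke is a plausible reason not to refill, so the events removed are not a random sample, while the matching event-free time is kept. The rates of both primary outcomes would be too low. The 14-day run changes the length of the gap but keeps the same dependence on the future.

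This matters because event rates with confidence intervals for each treatment are planned results in their own right (section 9.7.1), and section 9.5 describes the aim as estimation rather than a test of superiority.

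**Working it through.** **1. The rules side by side.** Count gap days from the end of supply, with a 30-day allowance.

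| Patient | Abstract: supply end | If the body means day 30 |
|---|---|---|
| Bleeds day 10, refills day 25 | bleed counts | bleed counts |
| Bleeds day 10, no refill or other censoring event by day 30 | censored day 0, bleed lost | bleed counts |
| Bleeds day 10, switches day 20 | gap never exceeds 30 days, bleed counts | bleed counts |
| No bleed, refills day 25 | 25 event-free days count | 25 event-free days count |

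The rules differ for these patients only in the second row. Within the abstract's list the earliest date governs, so supply end would apply even if the day of discontinuation were dated to day 30.

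**2. Inputs and the plan's own figures.** From section 9.5: 3.1% per year, mean follow-up 0.82 years, 10% matching loss, 1:1 matching, two-sided 0.05. That gives 16,000 × 0.9 = 14,400 and 6,000 × 0.9 = 5,400 per arm. With D = n × [(1 − exp(−0.031 × 0.82)) + (1 − exp(−0.031 × RR × 0.82))] events and power = Φ(½√D × ln RR − 1.96), the stated detectable differences are reproduced. For rivaroxaban, 22% gives 80.4% and 25% gives 88.9%. For apixaban, 37% gives 80.4% and 43% gives 90.0%. The power figures are not in question.

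Expected dabigatran major bleeds are 14,400 × 0.82 × 0.031 = 366 and 5,400 × 0.82 × 0.031 = 137.

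**3. Size under the abstract's date.** Let s be the share of counted person-time in bridged gaps, and q the share of gap events followed by a gap of more than 30 days. With a constant hazard, observed rate = true rate × (1 − q × s). Both s and q are assumptions.

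| s | q | Rate from 3.10% per year | Understatement |
|---|---|---|---|
| 2% | 0.5 | 3.07% | 1% |
| 5% | 0.5 | 3.02% | 2.5% |
| 5% | 1 | 2.95% | 5% |
| 10% | 0.5 | 2.95% | 5% |
| 10% | 1 | 2.79% | 10% |

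At s = 5% and q = 0.5 to 1, 366 × 0.025 to 366 × 0.05 is about 9 to 18 bleeds lost, and 137 × 0.025 to 137 × 0.05 is about 3 to 7.

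A refill simulation (2,000,000 patients per setting, mean bridged gap 2 to 10 days before the 30-day cap, q = 0.5 to 1) gave a downward bias in every setting: 0.7 to 7.8% with 90-day fills and 2.2 to 23.5% with 30-day fills. The spread shows how far the size depends on fill and gap lengths that the documents do not give. With supply end plus 30 days for everyone, the simulated rate was 3.06 to 3.13% against a true 3.10%.

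**4. Hazard ratio.** With the same q in both arms, the bias factor is (1 − q × s₁)/(1 − q × s₂).

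- Equal s: factor 1.
- Assumed s of 5% and 10%: 0.975/0.95 = 1.03 at q = 0.5, and 0.95/0.90 = 1.06 at q = 1.

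For scale, if the comparator has a similar number of bleeds, the standard error of the log hazard ratio is √(2/366) = 0.07 or √(2/137) = 0.12, larger than either shift on the log scale (0.03 and 0.05).

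**The case against.** The strongest reply is that the body already does the right thing. The supply-end item appears only in the abstract. Sections 9.2 and 9.7.1 define discontinuation as a gap that passes 30 days and censor there; the natural reading is day 30. The person-time lists stop at the first of the outcome or such a gap, so a bleed on gap day 10 comes first and counts. This reading is fair, and on it the bias is absent. It does not settle the matter, because the abstract then contradicts the body and its date is the only explicit one.

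Three further points stand in part.

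- **Size.** Section 9.4 describes very low patient cost for drugs, which suggests short gaps. A reader might infer double-digit event losses from the simulation's upper end, but nothing in the documents supports those gap lengths.
- **The remedy.** Section 7 says the drugs' effects wane within about a day, so the added days are largely off-drug. The simulation's agreement with 3.10% follows from assuming the same hazard off supply as on it. Suppose instead that every patient discontinues, 0.82 years (299.5 days) is supplied time, and off-drug bleeding is half as frequent. The rate is then (299.5 × 3.1 + 30 × 1.55)/329.5 = 2.96%, a 4.6% understatement. With 14 days it is (299.5 × 3.1 + 14 × 1.55)/313.5 = 3.03%, or 2.2%. The remedy has a bias of its own, but one that does not depend on later refills and that the 14-day run helps to show.
- **Redaction.** Detail of the sensitivity analyses is missing from the public copy, and another risk window may be defined there. That would not reconcile the main-analysis date.

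**Conclusion.** The point holds conditionally. If the abstract's date governs, rates of stroke and major bleeding are biased downward by about s × q, for example 2.5 to 5% at the assumed s = 5% and q = 0.5 to 1. If the body means day 30, there is no such bias but there is a contradiction. Either way the document does not fix one censoring date.

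Stronger readings that a reader might reach are not supported:

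- **That gap days count only if the patient refills.** A gap cut short within 30 days by a switch, dose change, disenrolment, study end or death never exceeds 30 days, so on a literal reading its days and events stay in.
- **That the most severe events are lost most.** Patients who bleed and then switch or die within 30 days are retained.
- **That the between-drug comparison is biased.** This needs s or q to differ between arms, and the documents give no sign of that. Once-daily against twice-daily dosing could be offered as a reason for rivaroxaban, but not for apixaban, which is twice daily like dabigatran.

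For all-cause mortality the direction depends on programming. It is upward if deaths in the gap are kept while discontinuers' gap time is dropped, and downward if every non-refill is cut at supply end.

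**What to change.** Reconcile section 4 (Length of Follow-up and Outcome Analysis), section 9.2 and section 9.7.1 to one date that does not depend on a later refill. On-treatment time ends at supply end plus the allowable gap (30 days; 14 in the sensitivity run) for every patient, unless an outcome, switch, dose change, disenrolment, death or study end comes first. Events up to that date count. Delete the supply-end item from the main analysis and report supply-end censoring as a sensitivity analysis, labelled as such.

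The cost is a sentence of text and the matching line of code. The price is up to 30 largely off-drug days of risk time per discontinuer, which may dilute the contrast or attribute off-drug events to the drug. The 14-day run, read beside the supply-end run, helps show how much. Tabulating the share of person-time in bridged gaps by arm would replace the assumed s with an observed value.
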